8.1.4 Subgroup Analysis of CDR-SB Score

To examine whether gender, age group, study site, country/geographic region or other baseline variables have an impact on response to treatment, subgroup analyses on CDR-SB score will be conducted on change from baseline to last observations up to Week 96. Subgroup analyses will be performed using an ANCOVA model with the terms of treatment, site, subgroup variable, the treatment-by-subgroup variable interaction, and baseline score as a covariate. The subgroup analysis for country/region will be performed using the same model but with the study site nested within geographic region. The hypothesis that consistent response to treatment across strata of a subgroup variable will be tested at the significance level of 0.100 by examining the P value of the treatment-by-subgroup interaction term in the ANCOVA model specified above. The statistical comparison of each ABBV-8E12 dose group with placebo within each stratum will be performed when the statistical significance of the treatment-by-subgroup interaction term is achieved at 0.100 level. The subgroup analysis will be conducted in the ITT data set.

8.1.5 Biomarker Research Analyses

CSF Concentration Variables

An ANCOVA will be performed on CSF concentrations for total tau, free tau, the ratio of free tau concentration to total tau concentration, and NFL for each scheduled time of evaluation during treatment (fourth dose interval and Week 96). For the analysis for the

fourth dose interval, an analysis will be performed for the data of Cohort 1 alone and also for all available data. The observations will be classified by treatment. The baseline value (last value before the first dose of study drug) will be the covariate except for the analysis on the ratio of the free tau and total tau concentrations, in which case the covariate will be the baseline total tau concentration measurement. If the probability distribution for a variable appears to have considerable non-symmetry (skewness coefficient > 0.75 in magnitude), a transformation will be sought so that the transformed variable has an approximately normal distribution. Within the framework of the ANCOVA the means of the four treatments (with adjustment for baseline) will be estimated. For each ABBV-8E12 dose level, the results of the test of the hypothesis of no difference between the dose and placebo will be reported. Also, with the motivation to have a test with good power if the dose response curve is a monotonic function of dose, a test will be performed on a contrast in the four treatment means. With μ_0 , μ_1 , μ_2 and μ_3 denoting the means for placebo, the 300 mg treatment, the 1000 mg treatment and 2000 mg treatment, respectively, the hypothesis that $-3\mu_0 - \mu_1 + \mu_2 + 3\mu_3 = 0$ will be tested at significance level 0.05 against the two-sided alternative hypothesis. The tests on the effects of the 1000 mg dose and the 300 mg dose will not be formally considered unless the statistic on the effect of the 2000 mg dose or the statistic on the contrast in the four means is significant at level 0.050.

Other CSF concentration variables of interest will be analyzed using methodology like that described for the analysis of total tau concentration.

Serum/Plasma Concentration Variables

Descriptive statistics will be provided for plasma concentrations of total tau and NFL. For each of these variables, an MMRM analysis will be performed on the data from the scheduled times of measurement. The model will include the baseline value as a covariate, have classification of subjects by treatment, an effect for time (classification) and will include an effect for the interaction of treatment and time of measurement. The initial model will also allow the regression coefficient for the baseline value to vary with time (an effect for interaction of time and the baseline value), but this feature will be

removed from the model if the statistic on this interaction is not significant at level 0.100. Within the framework of this model, the mean across the scheduled times of measurement and the mean for each individual time will be estimated for each treatment. Also, tests on differences of effect among the dose levels (with placebo considered a dose level) will be performed within the framework of the model. The primary tests will be on trend with dose (with placebo considered a dose level) and on the difference between the highest dose and placebo.

For total tau and NFL, the relationship to disease progression and response to treatment will be explored with disease state represented by CDR-SB score and perhaps by other variables of interest. The exploration on the relationship with disease progression will include an analysis of data from only the subjects treated with placebo.

Descriptive statistics and some or all of the analyses described here may be provided for other variables.

vMRI Variables

Descriptive statistics will be provided for the baseline value, for each scheduled time after that and for the changes from baseline. An analysis will be performed like that described for plasma NFL concentration, but with estimated total intracranial volume (eTIV) as a covariate in addition to the baseline value. The regression coefficient for eTIV will not vary with time, as may be allowed for the vMRI baseline value. An appropriate structure for the covariance matrix will be selected.

For each of whole brain, hippocampus and lateral ventricles, the relationship with the primary efficacy variable CDR-SB score, and possibly other efficacy variables, will be explored. The exploration will include an analysis of data from only the subjects treated with placebo. This may also be done for other regions.

Tau PET Scan Variables

For each region of the brain for which SUVR values are obtained, a joint analysis will be performed for the two scheduled times of evaluation during treatment (Week 44 and Week 96). The analysis will be like that described for plasma NFL concentration. For SUVR of selected regions, the relationship with the primary efficacy variable CDR-SB score will be explored. The exploration will include an analysis of data from only the subjects treated with placebo. This may be done also for other tau PET variables.

Consideration of Missing Values

The possibility of bias associated with missing data of subjects who prematurely discontinue treatment for reasons possibly related to study drug will be addressed.

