For CSF total tau and free tau concentrations and for their ratio, and for CSF NFL concentration, an analysis of covariance (ANCOVA) will be performed for each scheduled time of evaluation after treatment begins. The model will have classification of subjects by treatment. The covariate in these analyses will be the baseline value, except that for the analysis on the ratio of free tau and total tau concentrations, the covariate will be the baseline total tau concentration measurement. An MMRM analysis will be performed for plasma/serum concentration variables, vMRI variables, and tau PET variables for the scheduled measurements during treatment (ending at Week 96). For these analyses, the baseline value will be a covariate. Hypothesis testing on the effects of ABBV-8E12 doses will be done within the framework of the model. The primary tests will be a test on trend with dose (with placebo considered a dose level) and a test on the difference between the highest dose and placebo. The data will be transformed if there is a meaningful departure from the assumption of normality.

For some biomarker variables, the relationship to disease progression and response to treatment will be explored with disease state represented by the efficacy variable CDR-SB score and perhaps by some other variables. The exploration on the relationship with disease progression will include an analysis of data of only the subjects treated with placebo.

Statistical Methods (Continued):

Safety:

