An ANCOVA model will be used to evaluate CSF concentrations for total tau, free tau and the ratio of free tau concentration to total tau concentration for each scheduled time of evaluation during treatment (fourth dose interval and Week 96). For the analysis for the fourth dose interval, an analysis will be performed for the data of Cohort 1 alone and also for all available data. The observations will be classified by treatment. The baseline value for total tau and free tau (last value before the first dose of study drug) will be the covariate in the case of total tau and free tau, but for the analysis on the ratio the covariate will be the baseline total tau concentration measurement. If the probability distribution for a variable appears to have considerable non-symmetry (skewness coefficient > 0.75 in magnitude), a transformation will be sought so that the transformed variable has an approximately normal distribution. For each ABBV-8E12 dose level, the results of the test of the hypothesis of no difference between the dose and placebo will be reported. Also, with the motivation to have a test with good power if the dose response curve is a monotonic function of dose, a test will be performed on a contrast in the four treatment means. With μ_0 , μ_1 , μ_2 and μ_3 denoting the means for placebo, the 300 mg treatment, the 1000 mg treatment and 2000 mg treatment, respectively, the hypothesis that $-3\mu_0 - \mu_1 + \mu_2 + 3\mu_3 = 0$ will be tested at significance level 0.050 against the two-sided alternative hypothesis. The tests on the effects of the 1000 mg dose and the 300 mg dose will not be formally considered unless the statistic on the effect of the 2000 mg dose or the statistic on the contrast in the four means is significant at level 0.050.

CSF NFL concentration will be analyzed as described above for CSF total tau concentration. The same will be done for other CSF concentration variables for which data are reported, provided that the proportion of measurements that are outside the limits of quantification and the magnitude of the lower limit do not make a conventional analysis of covariance inappropriate.

Analysis of Serum/Plasma Concentration Variables

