For each region of the brain for which SUVR values are obtained, a joint analysis will be performed for the two scheduled times of evaluation during treatment (Week 44 and Week 96). The analysis will be like that described for plasma NFL concentration with some additional assumptions made. The model will be that of a MMRM analysis even though there are only two times of measurement. The baseline value will be a covariate, with the regression coefficient assumed to be the same for the two times of measurement. Compound symmetry will be assumed for the covariance matrix of the error terms of the two times of measurement. If data are reported for other continuous variables that reflect the extent of tau pathology, a similar approach will be used for their analysis.

Consideration of Premature Discontinuations

The possibility of bias from missing data of subjects who prematurely discontinue for reasons possibly related to study drug will be addressed. If it is concluded that there may be a bias of meaningful magnitude as a result of premature discontinuation, sensitivity analyses may be carried out. Also, some imputation of missing values for subjects who prematurely discontinue might be done.

Relationship with Disease State

For some of the exploratory biomarker variables, an analysis will be performed to explore the relationship to disease state/progression. Disease state will be represented by CDR-SB score, and explorations may be carried out on the relationship between the biomarker variables and other measures of disease level. The biomarker variables will include, but not necessarily be limited to, plasma total tau concentration, plasma NFL concentration, and the vMRI measures for whole brain, hippocampus, temporal lobe and lateral ventricles. The relationship between change in CDR-SB score and change in biomarker will be explored.

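### CSF tau and NFL get a separate ANCOVA at each visit, so subjects with fourth-dose CSF but no Week 96 CSF contribute nothing to the Week 96 contrast

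*Protocol*

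**What the plan says.** Four CSF variables are analysed: total tau, free tau, the free-to-total ratio, and NFL. The protocol synopsis says that an ANCOVA "will be performed for each scheduled time of evaluation after treatment begins". Protocol 8.1.5 names the two times in the words "NFL for each scheduled time of evaluation during treatment (fourth dose interval and Week 96". On the covariate it says "The baseline value (last value before the first dose of study drug) will be the covariate except for the analysis on the ratio"; for the ratio, baseline total tau is used instead.

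SAP 13.0 keeps this method: "An ANCOVA model will be used to evaluate CSF concentrations for total tau, free tau". The same two occasions reappear there, in this wording: "ratio of free tau concentration to total tau concentration for each scheduled time of evaluation during treatment (fourth dose interval and Week 96". On NFL the SAP adds: "CSF NFL concentration will be analyzed as described above for CSF total tau concentration". Neither document contains a repeated-measures model for CSF.

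The other biomarkers are handled differently. The synopsis states: "An MMRM analysis will be performed for plasma/serum concentration variables, vMRI variables, and tau PET variables for the scheduled measurements during treatment". For tau PET, which like CSF has two on-treatment times, SAP 13.0 says: "The model will be that of a MMRM analysis even though there are only two times of measurement".

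On missing biomarker data, protocol 8.1.5 promises only that possible bias from discontinuation will be addressed. SAP 13.0 allows sensitivity analyses and some imputation as options, with no method given.

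**The concern.** With baseline as the only covariate, the Week 96 ANCOVA is a complete-case analysis. The fourth-dose value of a subject without Week 96 CSF is not used at all. The contrast stays unbiased only if, given treatment and baseline, missingness at Week 96 is unrelated to what was seen at the fourth dose.

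Some missing Week 96 CSF can be foreseen. Under Lumbar Puncture in protocol 5.3.1.1, the final puncture is taken only if the final dose falls at least 3 months after the previous puncture, so some early discontinuers will have a fourth-dose sample and nothing later. Punctures are optional in Cohort 2, and the pandemic provisions let them be deferred.

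Protocol 8.1.10 names CSF free and total tau as target-binding markers and CSF NFL as a marker of pharmacodynamic activity. Week 96 is the only scheduled long-term CSF time. For CDR-SB, SAP 10.6 defends the MMRM because it suits data missing at random. The Week 96 CSF ANCOVA lacks that protection where missingness follows the fourth-dose value, and the plan gives no reason for treating CSF differently.

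**Working it through.** The documents state no sample size, power or precision for CSF, so there is no figure to reproduce. The check sizes the consequence under stated assumptions.

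**Inputs**
- m: fraction with fourth-dose CSF but no Week 96 CSF. Not in the documents; 0.25 and 0.40 are used as examples.
- rho: correlation of fourth-dose and Week 96 values after baseline adjustment. Not in the documents; range 0.3 to 0.9.
- Arm size: 12 per arm is Cohort 1 alone (48 / 4). The number of Cohort 2 volunteers is unknown, so 25 and 100 per arm were also simulated; 100 is the whole arm.

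**Precision.** For two normal measurements with the later one missing in a fraction m (monotone pattern, missing at random), the factored likelihood gives

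Var(joint) / Var(ANCOVA) = 1 − m × rho²

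| rho | m = 0.25 | m = 0.40 |
|---|---|---|
| 0.3 | 1 − 0.25 × 0.09 = 0.978 | 1 − 0.40 × 0.09 = 0.964 |
| 0.5 | 0.938 | 0.900 |
| 0.7 | 0.878 | 0.804 |
| 0.8 | 0.840 | 0.744 |
| 0.9 | 0.797 | 0.676 |

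In effective sample size (1/ratio − 1), this is a gain of 2% to 25% at m = 0.25 and 4% to 48% at m = 0.40. At m = 0 the ratio is 1: with complete data, the two-time model with unstructured covariance and baseline-by-time returns the ANCOVA's Week 96 estimate.

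Simulation at 12 per arm, with missingness unrelated to the values, gave 0.953 and 0.830 at m = 0.25 (rho 0.5, 0.8), and 0.934 and 0.743 at m = 0.40. The largest departure from the formula is 0.934 against 0.900: estimating the between-time slope costs a little in small groups.

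**Bias.** In the illustrative case, missingness at Week 96 in the active arm depends on the fourth-dose value with log-odds slope 1 per SD. Here m is the missing probability at the mean fourth-dose value. Results at 12 per arm, in residual SD:

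| m | rho | ANCOVA bias | SD of ANCOVA contrast | Joint-model bias |
|---|---|---|---|---|
| 0.25 | 0.5 | −0.119 | 0.474 | 0.000 |
| 0.25 | 0.8 | −0.187 | 0.471 | 0.004 |
| 0.40 | 0.5 | −0.174 | 0.549 | 0.002 |
| 0.40 | 0.8 | −0.274 | 0.534 | 0.006 |

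The ANCOVA bias hardly changes with arm size: at 100 per arm it is −0.118, −0.197, −0.174 and −0.273. The sign follows the assumed direction of the dependence. Relative to the SD of the contrast, the bias runs from 0.119/0.474 = 0.25 to 0.274/0.534 = 0.51 at 12 per arm. At 100 per arm it runs from 0.118/0.166 = 0.71 to 0.273/0.179 = 1.53.

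**The case against.** The case for leaving the plan alone has real weight.

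- **Timing.** The fourth-dose puncture is about 14 days after a dose, while Week 96 is four weeks after Dose 24. Protocol 5.6.4 predicts that CSF tau binding at 300 mg varies from about 30% to 55% between trough and peak, so the two times reflect different exposure. This stands as a reason not to assume a common effect. It does not require separate models, because treatment-by-time lets each visit have its own contrast.
- **Small, assumed gain.** At rho 0.3 to 0.5 and m = 0.25 the variance falls by only about 2% to 6%. The bias example needs arm-specific, value-dependent missingness, which nothing in the documents predicts. At 12 per arm it is at most about half the SD of the contrast. This stands, and limits the weight of the point.
- **m may be low.** The Appendix C column is for completion or premature discontinuation, so many discontinuers may have a later puncture. But SAP version 3.0 removed the CSF analysis windows (SAP 14.0), so whether such a puncture counts as Week 96 is undefined.
- **Missing data are mentioned.** They are, but without a method.
- **Exploratory status.** The CSF effects are exploratory objectives outside the family-wise error control in SAP 10.7. The target-engagement interim uses Cohort 1 under a separate biomarker plan. No decision in these documents rests on the Week 96 CSF contrast.

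A reader might also infer more than the documents support:
- That subjects with both punctures lose precision because their fourth-dose values are ignored. They do not; the gain comes only from subjects lacking the later value.
- That the plan expects 25% loss of Week 96 CSF, leaving about 9 per arm. The 25% in protocol 8.2 and SAP 4.3 belongs to the CDR-SB power assessment and concerns subjects with no post-baseline data. Read literally for CSF, they would have no fourth-dose value to recover either. Nine per arm would also be a Cohort 1 count, whereas the Week 96 analysis is not restricted to Cohort 1.
- That CSF is the smallest biomarker data set. SAP 14.0 says tau PET numbers are now expected to be substantially smaller than anticipated, and the number of Cohort 2 CSF volunteers is not given.

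**Conclusion.** The point holds in a limited form. Both documents specify visit-by-visit ANCOVA for CSF, which discards fourth-dose-only subjects at Week 96 and leaves that contrast exposed if missingness follows the fourth-dose value. The sponsor already uses a joint model for every other longitudinal biomarker, including one with two visits.

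The size rests on assumed m and rho. The variance reduction is about 2% to 20% at m = 0.25 and 4% to 32% at m = 0.40 for rho 0.3 to 0.9, and nil if no Week 96 CSF is missing. The bias of 0.12 to 0.27 residual SD is an illustration of one mechanism, not a prediction, and the joint model removes it only under missing at random. Nothing here shows that the Week 96 CSF result will be biased, and the primary and key secondary analyses are untouched. This is a worthwhile, low-cost improvement to an exploratory analysis.

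**What to change.** In protocol 8.1.5 (and the synopsis) and SAP 13.0, replace the two all-data CSF ANCOVAs with one MMRM on the fourth-dose and Week 96 values of each variable. Include treatment, time, treatment-by-time, baseline (baseline total tau for the ratio) and baseline-by-time, with an unstructured 2×2 covariance. Report the same dose-versus-placebo and trend contrasts at each time. Unstructured covariance is preferable here to the compound symmetry used for tau PET, because it preserves the ANCOVA result when data are complete.

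Keep the Cohort-1-only fourth-dose ANCOVA as it stands. State which premature-discontinuation punctures count as Week 96. Name the visit-by-visit ANCOVA as the fallback if the model does not converge.

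The cost is SAP wording and a short program. The downsides are one extra parameter (the between-time covariance; the two ANCOVAs already estimate two residual variances) and the need for one transformation that suits both times.

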8.1.6 Safety Analyses

All safety analysis will be performed on the safety data set unless otherwise specified. Comparisons between each ABBV-8E12 dose group and placebo will be performed with two-sided test at the significance level of 0.05, if applicable. Pairwise comparisons for each ABBV-8E12 dose group versus placebo will be evaluated.

All safety assessments that are taken no more than 20 weeks after the last dose of study drug will be included in the safety evaluation for subjects who complete the double-blind Treatment Period or PD and do not roll over to the planned extension study. If subjects enroll in the planned extension study, their safety information collected before the first dose of the planned extension study will be included in the safety evaluation for the double-blinded period.

Study Drug Exposure and Compliance

The number of doses on study drug will be summarized by treatment group and all treatment groups combined. The number and percentage of subjects with at least 90% compliance with study drug (i.e., complete 90% of scheduled doses) will be summarized by treatment group and all treatment groups combined.

Adverse Events

A treatment-emergent adverse event (TEAE) is defined as any adverse event that begins or worsens in severity on or after the first study drug dose date and no more than 20 weeks after the last study drug dose date.

Unless otherwise specified, the treatment group differences in continuous safety variables (e.g., change from baseline to final observation on laboratory tests) will be assessed using an ANOVA model with the term of treatment, and the treatment group differences in binary safety variables will be evaluated using a Fisher's exact test.

8.1.6.1 Analysis of Adverse Events

Adverse events will be coded using the most current version of the Medical Dictionary for Regulatory Activities (MedDRA). The number and percentage of subjects who report TEAEs will be tabulated by MedDRA system organ class (SOC) and preferred term (PT) for each treatment group, overall ABBV-8E12 and all treatment groups combined. Treatment group differences between each ABBV-8E12 dose group and placebo will be analyzed using Fisher's exact test.

The number and percent of subjects experiencing treatment-emergent SAEs (including deaths) and adverse events leading to premature discontinuation of study drug will be tabulated by MedDRA SOC and PT for each treatment group, overall ABBV-8E12 dose groups, and all treatment groups combined. Treatment group differences between each ABBV-8E12 dose group and placebo will be analyzed using Fisher's exact test.

